### **3. Methods**

It will be a prospective, single blinded, randomized clinical trial, performed at Center of Research of the Department of Speech Therapy, Physical Therapy and Occupational Therapy of São Paulo University.

Forty chronic stroke patients will be randomly in control and experimental group, 20 each one. Both groups conduct 14 training sessions, twice a week, for seven weeks. Each session will consist a 30 minute-global-exercise series including stretching, muscle strength and axial mobility exercises. After this, both groups will perform 30 more minutes of balance training using eight Wii Fit® games which stimulate motor and cognitive functions.

Patients will be assessed at the beginning, in the end and 60 days after the end of the treatment (follow-up).

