### **3.2 Procedures**

#### **3.2.1 Assessments**

Both groups will be assessed before treatment, after treatment and after 60 days of the end of the treatment (follow-up).

Primary outcomes:

- The lower limb subscale of the Fugl-Meyer Assessment (FMA-LE): FMA-LE is a subscale measuring lower limb motor recovery. It examines movement and coordination of the hip, knee, and ankle in the supine, sitting, and standing positions. Each item is scored on a 3-point scale (0, cannot perform; 1, partially performs; 2, performs fully). The score range is 0 to 34, with higher scores indicating better lower limb motor performance (Fugl-Meyer, 1975; Maki, 2006).
- Balance Evaluation Systems Test (BESTest): Balance Evaluation Systems Test (BESTest) measures balance. It includes 36 items that evaluate performance of
  - 6 balance systems: biomechanical constraints, stability limits/verticality, anticipatory postural adjustments, postural responses, sensory orientation, and stability in gait (Horak, 2009).
  - 6-minute walk test: The 6MWT is a practical simple test. This test measures the distance that a patient can quickly walk on a flat, hard surface in a period of 6 minutes (the 6MWD). The 6MWT has been used as a measure of functional status of patients (Britto, 2006).

Secondary outcomes:

- Limits of Stability: The Limits of Stability subtest quantifies the maximum distance a person can intentionally displace their center of pressure (COP) from start position of midline COP centered over the base of support to eight targets.

Location and movement of the COP was indicated by a cursor display projected on a screen in front of the subject. As targets were highlighted, the subject was to move the COP cursor quickly and accurately as possible towards a target located on the Limits of Stability perimeter and hold position as close to the target as possible. The parameters include COP movement velocity and directional control (% to target).

- Rhythmic Weight Shift: The Rhythmic Weight Shift quantifies the subject's active weight shift ability by moving the COP cursor to match velocity and direction of a moving visual target in the medial- lateral (ML) and anterior-posterior (AP) directions at three different velocities.

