### **3.2.2 Training**

Both groups will participate of 14 individual treatment sessions, with physiotherapist supervision, twice a week, for seven weeks. Each treatment session will be composed of 30 minutes of regular physical therapy (equal to both groups), based on stretching, strength and mobility exercises, followed by 30 minutes of balance training using a gaming system with balance board device (eight games of Nintendo Wii Fit®, for games per session).

Differences between groups are based on the type of physiotherapist's role in the training:

Virtual Reality Training Without Physiotherapeutic Intervention (Experimental Group) will perform a balance training program in a virtual environment (using a gaming system with balance board device - eight games of Nintendo Wii Fit®, for 14 sessions)

without verbal/manual physiotherapeutic intervention. Initially, physiotherapist will provide instructions about the rules and strategies of how to play the game and control the avatar. Then the patient will be invited to start the game, and in the two attempts of the training no manual or verbal assistance will be provided by the physiotherapist. Physiotherapist participation during training will be restricted to ensuring patient safety, providing motivational verbal stimuli, and replicating the feedback provided by the game at the end of each attempt.

Virtual Reality Training With Physiotherapeutic Intervention (Control Group) will perform a balance training program in a virtual environment (using a gaming system with balance board device - eight games of Nintendo Wii Fit®, for 14 sessions) with verbal and manual physiotherapeutic intervention. Initially, physiotherapist will provide instructions about the rules and strategies on how to play the game and control the avatar. Then the patient will be invited to start the game, and in the first attempt of the training physiotherapist will provide manual and verbal assistance, providing corrections on movement speed, direction, acceleration, amplitude, rhythm and coordination, necessary to achieve game goals (avoiding compensatory movements). In the second attempt, no manual or verbal assistance will be provided by the physiotherapist (only ensuring patient safety and providing motivational verbal stimuli, and replicating the feedback provided by the game), allowing the patient to organize his or her performance.

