### **3.3 Statistical Analysis**

Demographic data and clinical characteristics of the control and experimental groups will be compared using the unpaired T-test.

Results of the primary and secondary measures will be analyzed after normality test (Kolmogorov-Smirnov test), with repeated measures of variance (ANOVA), one for each dependent variable, using as a factor group (GC and GE) and the three evaluations (before treatment, after treatment and follow up), the last measure being repeated (2x3 RM-ANOVA).

The Tukey Post Hoc Test will be performed to verify any differences between effects with significance.

Significance level adopted: 5%.

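### The three-visit RM-ANOVA, with no missing-data rule, discards the observed post-treatment result of any patient who misses the 60-day visit; a mixed model on all observed visits would keep it

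*Combined protocol and SAP*

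**What the plan says.** - Section 3. Methods sets the size: "Forty chronic stroke patients will be randomly in control and experimental group, 20 each one".
- The same section sets three assessments: "Patients will be assessed at the beginning, in the end and 60 days after the end of the treatment (follow-up"). Section 3.2.1 Assessments repeats this schedule for both groups.
- Section 3.2.2 Training gives both arms the same contact: "Both groups will participate of 14 individual treatment sessions, with physiotherapist supervision, twice a week, for seven weeks".
- Section 3.3 Statistical Analysis names one analysis for all primary and secondary measures, "with repeated measures of variance (ANOVA), one for each dependent variable", with group as one factor and, as the other, "the three evaluations (before treatment, after treatment and follow up), the last measure being repeated (2x3 RM-ANOVA"). A Tukey post hoc test follows, at a 5% significance level.

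The combined protocol and SAP contains no analysis population, rule for replacing patients, imputation rule, dropout allowance or sensitivity analysis. It names no primary time point and has no separate analysis of the post-treatment visit.

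**The concern.** The classical 2x3 RM-ANOVA splits each patient's variation over the three visits, so it needs all three values. The plan does not write out case deletion. Deletion follows from the named method combined with silence about missing values. The patient most affected is one who has completed treatment and has a post-treatment measurement but does not return 60 days later. That measurement bears directly on the aim in section 2. Purpose, yet it would be discarded because of a later absence.

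The certain cost of any such absence is lost precision, in a trial with only 20 patients per arm. A possible further cost is bias. That arises only if missing the visit is related to outcome and the relation differs between arms. Since both arms receive the same number of supervised sessions, arm-specific dropout is an assumption. There is also a procedural cost: with no rule in the plan, the handling of the first missed visit would be decided after data have been seen.

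A secondary point is that the uncorrected F test for visit and group-by-visit assumes sphericity, and the plan names no correction.

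**Working it through.** **Inputs.** From the documents: 40 patients, 20 per arm, three visits, 5% significance (taken as two-sided). The plan states no effect size, SD, power or dropout, so there is no planned figure to reproduce. Assumptions: a fraction d of each arm (5%, 10%, 15% or 20%) misses only the 60-day visit; correlation between visits is rho = 0.7, with 0.8 as a check.

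**1. Does the method lose the patient?** In a software check, one 60-day value was removed from simulated data on 40 patients. A standard RM-ANOVA routine refused the data as unbalanced. A linear mixed model used all 40 patients and 119 of the 120 observations.

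**2. Precision of the post-treatment contrast.** Patients analysed = 40(1 − d). SE factor = 1/√(1 − d). Power is from the noncentral t for a two-sample comparison of change. The effect is fixed at 0.909 SD of change, which has 80.0% power at 20 per arm.

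| d | Per arm | Analysed | SE factor | Power |
|---|---|---|---|---|
| 0% | 20 | 40 | 1.000 | 80.0% |
| 5% | 19 | 38 | 1.026 | 77.8% |
| 10% | 18 | 36 | 1.054 | 75.5% |
| 15% | 17 | 34 | 1.085 | 72.9% |
| 20% | 16 | 32 | 1.118 | 70.1% |

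A simulation with 20 per arm and 1 to 4 missed 60-day visits per arm gave complete-case to all-available SE ratios of 1.02 to 1.12 at post-treatment and 1.01 to 1.05 at 60 days.

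**3. Bias under one assumed mechanism.** Suppose the chance of missing the visit follows a probit with slope 1 per SD of post-treatment change in one arm and is random in the other, with equal total loss. With k = Φ⁻¹(1 − d), the complete-case bias in the difference in change, in outcome SD, is

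0.5 × √2 × φ(k)/(1 − d) × √(2(1 − rho)).

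For d = 15% and rho = 0.7: k = 1.036, φ(k) = 0.2332, and 0.7071 × 0.2332/0.85 × 0.7746 = 0.150.

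| d | Bias in change, rho 0.7 | Bias in change, rho 0.8 | Bias in raw post-treatment difference, rho 0.7 |
|---|---|---|---|
| 5% | 0.059 | 0.049 | 0.03 |
| 10% | 0.107 | 0.087 | 0.05 |
| 15% | 0.150 | 0.123 | 0.075 |
| 20% | 0.192 | 0.157 | 0.10 |

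At 15% loss the SE of the change contrast with 17 per arm is √(0.6 × 2/17) = 0.266, so the bias is 0.150/0.266 = 0.57 of an SE. Simulation at 15% gave 0.150 for this mechanism, 0.000 for random dropout and −0.001 when the same mechanism acts in both arms. A different illustrative mechanism (logistic, rho 0.8) gave 0.12 to 0.34 SD of change over nominal rates of 5% to 25%, so the size depends on the mechanism chosen. In that simulation, using all observed post-treatment data gave bias near zero.

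**4. Sphericity.** Type I error of the uncorrected group-by-visit F test (2 and 76 df), by correlation of visits 1–2, 1–3 and 2–3:

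| Correlations | Epsilon | Type I error |
|---|---|---|
| 0.80/0.75/0.85 | 0.92 | 5.3% |
| 0.70/0.65/0.80 | 0.91 | 5.4% |
| 0.85/0.80/0.90 | 0.87 | 5.6% |
| 0.70/0.65/0.85 | 0.83 | 5.8% |
| 0.80/0.75/0.90 | 0.81 | 5.9% |
| 0.70/0.65/0.95 (extreme) | 0.61 | 7.4% |

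With epsilon-adjusted degrees of freedom all six are 4.8–4.9%.

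**The case against.** **Deletion is inferred.** The plan never says that incomplete patients are removed, and an imputation rule could avoid it. That is true, but no such rule exists, and choosing one after the data are in is what a SAP should prevent.

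**The cost is conditional.** All patients are scheduled for all visits, and at 5–10% loss the SE penalty is only 3–5%. Patients lost during the seven weeks have no post-treatment value to rescue. This stands, and it limits the size of the point.

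**The power series is not for the planned test.** It uses a t-test on change. With the pooled RM-ANOVA error under sphericity (4n − 4 df for n per arm), the same effect has 81% power at 20 per arm and 79%, 77%, 74% and 72% at 19, 18, 17 and 16. The levels move by 1 to 1.5 points and the decline is nearly the same.

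**The replacement has a price.** For the joint group-by-visit test with complete data and true sphericity, an effect with 80% power by RM-ANOVA (2, 76 df) has about 78% under an unstructured covariance (2, 37 df). At 5% missing, complete-case RM-ANOVA has 77.7%, so the gain is at most about half a point. At 15% it is 72.5% against at most 78%. This also stands, but it concerns one covariance choice, and a more economical structure may be justified in advance.

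**A narrower remedy would do.** Analysing post-treatment change in everyone who has that visit would also keep the data. It is a reasonable alternative. The mixed model covers both time points in one pre-specified analysis.

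**Conclusion.** The concern holds. The structural gap is certain: the only named analysis needs three complete visits, and nothing in the plan says what happens otherwise. Its size depends on attendance, which the documents do not predict. For 5% to 20% missing only the 60-day visit, the SE of the post-treatment contrast is 3% to 12% larger, and 80% power becomes 77.8% to 70.1%. With full attendance the loss is zero.

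The bias figures illustrate one assumed one-arm mechanism and should not drive the decision. Sphericity is minor: the error is 5.3–5.9% in the plausible patterns. This is a change that should be made because it is cheap and protects data already collected. Full attendance would leave the trial's conclusions unaffected by this point.

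**What to change.** In section 3.3, replace the RM-ANOVA with wording such as:

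> Each outcome will be analysed by a linear mixed model for repeated measures (REML) with group, visit and group-by-visit, including every randomised patient in the assigned group and all observed visits. Group differences in change at post-treatment and at 60 days will be estimated from this model.

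Also state in advance:

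- the covariance structure and degrees-of-freedom method, for example unstructured with Kenward-Roger (other justified choices are acceptable);
- that any post hoc comparisons use the model means;
- that the number missing each visit will be reported by arm;
- two sensitivity analyses: (a) the complete-case RM-ANOVA with Greenhouse-Geisser correction; (b) non-ignorable dropout, for example a shift applied to missing 60-day values in one arm at a time.

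**Cost.** SAP wording and standard software; no new data, visits or patients. The model relies on missing at random. An unstructured covariance has 6 parameters against 2 for compound symmetry, estimated from 40 patients. The SE gain at 60 days is only about 1–5%. If dropout depends on the unseen 60-day change in one arm (15% loss), simulation shows the mixed model still biased by 0.08–0.11 SD at 60 days, against 0.14–0.16 SD for complete cases. A stronger mechanism would leave more, which is why analysis (b) is needed.

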#### **3.1 Participant allocation**

Patients will be randomized in two groups: Experimental Group or Control Group. Each participant must sign the Consent Form.

Forty patients will be selected according to the following criteria:

Inclusion Criteria:

- hemiparetic status resulting from a single stroke at least 6 months earlier;
- the ability to walk 10 m independently with or without an assistive device;
- a Montreal Cognitive Assessment (MoCA) score of  $\geq 20$ ;
- the absence of a musculoskeletal condition that could potentially affect the ability to stand or walk safely;
- absence of serious visual impairment or a hearing disorder;
- muscle strength  $\geq 3$  in lower limbs;
- ability to understand and follow simple instructions.

Exclusion Criteria:

- severe dementia or aphasia;
- hemispatial neglect, ataxia or any other cerebellar symptom;
- inability to stand without minimal assist;
- uncontrollable medical complications;
- participation in other studies or rehabilitation programs.

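### Visit-specific group differences would be better drawn from two baseline-adjusted contrasts than from Tukey comparisons after the 2x3 repeated-measures ANOVA

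*Combined protocol and SAP*

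**What the plan says.** Section 3.3 (Statistical Analysis) plans a repeated-measures ANOVA, "one for each dependent variable", "using as a factor group (GC and GE) and the three evaluations (before treatment, after treatment and follow up"), with "the last measure being repeated (2x3 RM-ANOVA"). The post hoc rule is one sentence: "The Tukey Post Hoc Test will be performed to verify any differences between effects with significance". The level is 5% ("Significance level adopted: 5"%), with no allocation over effects, visits or outcomes.

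The design is in section 3: "Forty chronic stroke patients will be randomly in control and experimental group, 20 each one". The visits are in section 3.2.1: "Both groups will be assessed before treatment, after treatment and after 60 days of the end of the treatment (follow-up"). Section 2 (Purpose) asks for a comparison of training with and without the physiotherapist's intervention and ties it to no visit. Neither post-baseline visit is named as primary. Apart from its place as the first level of the repeated factor, the baseline value of an outcome is not used in the group comparison.

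**The concern.** The ANOVA has three testable effects: group, evaluation and their interaction. The Tukey sentence implies that some effect must be significant first, but it does not say which effect opens which comparisons. The family could be two group means, three visit means or six cell means, and no error term is given.

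The interaction test can show that the groups' courses differ. It cannot say whether they differ at the end of treatment, at 60 days or at both, or by how much. Any such statement would rest on the Tukey step. If that step is run on the six group-by-visit cells, it spreads the error rate over 15 pairs, ignores a baseline that is already collected, and needs one error term for pairs that have different variances. The likely result is a significant interaction that the post hoc step cannot locate.

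**Working it through.** The plan gives no power, effect size, SD or between-visit correlation, so it has no figure of its own to reproduce.

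**Inputs.** From the documents: 20 per arm, three visits, two groups, 5% level. Assumed: SD 1, complete data, compound symmetry with rho 0.5, 0.7 or 0.9, two-sided tests, effects of 0.5 or 0.8 SD.

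**1. Family.** Six cells give 6 x 5 / 2 = 15 pairs. Three are same-visit group differences, and one of those three is at baseline. Two are left that bear on the aim.

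**2. Error term.** Variances below are in SD units.
- Same-visit group difference: 2/n.
- Before/after difference within a group: 2(1 - rho)/n.
- The within-patient mean square estimates 1 - rho. The pooled mean square estimates [(1 + 2rho) + 2(1 - rho)]/3 = 1.
- Within-patient error therefore makes the standard error of a same-visit group difference too small by sqrt(1 - rho) = 0.71, 0.55, 0.32. Pooled error suits those pairs but is too large for before/after pairs by 1/sqrt(1 - rho). No single term suits all 15.

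**3. Critical values (t scale).** Tukey on six means: 2.92 with 76 df, 2.90 with 114 df. Baseline-adjusted contrast with 37 df: 2.03 at 5%, 2.34 at 2.5%.

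**4. Power after treatment by hand, 0.5 SD.** The unadjusted standard error is sqrt(2/20) = 0.316, so the standardised effect is 0.5/0.316 = 1.58.
- Pooled Tukey, before any gate: P(Z > 2.92 - 1.58) = P(Z > 1.34), about 9%.
- Baseline-adjusted: the standard error is 0.316 x sqrt(1 - rho²) = 0.274, 0.226, 0.138, so the standardised effects are 1.83, 2.21, 3.63. At 5%, P(Z > 0.20), P(Z > -0.18), P(Z > -1.60) = about 42, 57, 95%. At 2.5%, P(Z > 0.51), P(Z > 0.13), P(Z > -1.29) = about 30, 45, 90%.

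**5. Simulation** (20,000 to 40,000 trials per setting; Tukey on six cells, opened only by a significant interaction). Runs agree to about one point.

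| Sustained 0.5 SD | rho 0.5 | rho 0.7 | rho 0.9 |
|---|---|---|---|
| Pooled Tukey, group difference after treatment | 6% | 7% | 10% |
| Baseline-adjusted contrast at 5% | 41% | 57% | 94% |
| Baseline-adjusted contrast at 2.5% | 30% | 45% | 89% |
| Interaction F test | 34% | 53% | 96% |
| Significant interaction, but pooled Tukey finds neither later visit | 72% | 79% | 86% |

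At a sustained 0.8 SD the last row is 42, 50 and 57%.

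**6. Where the gain comes from** (rho 0.7, 0.5 SD, 5% level). Pooled Tukey behind the gate 7%, unadjusted t-test 34%, baseline-adjusted 57%. So 34 - 7 = 27 points come from dropping the 15-pair family and the gate, and 57 - 34 = 23 from baseline adjustment.

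**7. Error control with no effect.** Ungated pooled Tukey flags either later visit in 0.6 to 0.8% of trials. The two contrasts at 2.5% each do so in 4.7 to 4.9%.

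**8. The other error term.** Suppose within-patient error were used and a 0.8 SD effect were present after treatment only. Follow-up would be flagged in about 3, 11 and 35% of trials, and both visits in about 2, 6 and 30%. The adjusted contrast at 2.5% flags follow-up in 2.4 to 2.5%.

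**The case against.** The strongest reply is that the main inference is intact. Section 2 names no visit, and the group-by-time F test answers whether the groups' changes differ. At rho 0.7 its power is 53% for 0.5 SD and 92% for 0.8 SD, close to the 57% and 93% of the adjusted contrast at 5%. The plan is under-specified rather than wrong: one sentence naming gate, family and error term would close the gap, and choosing ANCOVA over Tukey is partly preference. Every size above rests on a correlation and an effect that the documents do not give.

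Most of this stands. The visit-specific question is inferred from the aim and the visit schedule, and the gain is confined to that statement. But naming the family and error term would not recover the power lost to 15 pairs, nor use the baseline.

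Three stronger readings are tempting, and the documents support none of them.
- **That the plan inflates false positives.** If a significant evaluation effect also opened the six cells and within-patient error were used, a false group difference at a later visit would appear in about 7, 18 and 45% of trials. Section 3.3 states neither the family, nor that error term, nor that gate. With pooled error, false positives are controlled.
- **That the power loss and the false follow-up findings both apply.** They come from alternative error terms, so at most one can occur.
- **That the 3, 11 and 35% are trials flagged at follow-up and nowhere else.** They count every follow-up flag. Follow-up without an after-treatment flag is about 2, 4 and 5%. A difference wrongly reported as lasting needs both visits flagged, and that is large only at high correlation.

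**Conclusion.** The point holds as a cheap improvement. The group-by-time F test is not disputed, nor is Tukey on the three time means, both under sphericity. The step that locates and sizes the group difference is weak if Tukey is run on the six cells, which is one natural reading but not the only one. With pooled error it is safe but has little power: about 6 to 10% after treatment for a sustained 0.5 SD effect, against 30 to 89% for a baseline-adjusted contrast at 2.5%. It leaves roughly 72 to 86% of significant interactions without a group difference at either later visit. These figures assume compound symmetry, complete data, 20 per arm and rho between 0.5 and 0.9. A check without compound symmetry (adjacent visits 0.8, first to last 0.7) gave 81% for the last figure.

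**What to change.** For each outcome, replace Tukey on the group-by-visit cells with two pre-specified between-group contrasts, after treatment and at 60 days. Adjust each for that outcome's baseline value, by ANCOVA per visit or an equivalent mixed model on the two later visits with group, visit, group-by-visit, baseline and baseline-by-visit. State that the contrasts do not depend on a significant interaction, and report the group-by-time F test as the supporting global test.

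The documents do not rank the two visits, so split the level: 2.5% each, with 97.5% confidence intervals. Use a fixed sequence only if the sponsor names after treatment as the primary visit. At rho 0.7 and 0.5 SD, a fixed sequence starting there confirms a follow-up-only effect in 3% of trials (45% with the split) and a sustained effect at follow-up in 38% (45% with the split).

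Tukey may stay for the three time means, after a significant evaluation effect and with the within-patient error term. Other cell comparisons and within-group changes become descriptive and are not used to infer a group difference.

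The cost is SAP wording, with no new data or visits. Other cell comparisons lose confirmatory status. Testing at 2.5% rather than 5% costs 41 - 30 = 11, 57 - 45 = 12 and 94 - 89 = 5 points of power per contrast at 0.5 SD. The split covers the two visits within one outcome and does not address multiplicity across the three primary outcomes, which is a separate matter.
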